IND	Investigational New Drug
IR	immediate release
IRB	Institutional Review Board
IWRS	interactive web response system

MAR	Missing at Random
MedDRA	Medical Dictionary for Regulatory Activities
MI	multiple imputation
MIDAS	Migraine Disability Assessment
MMD	monthly migraine day
MMRM	Mixed Model for Repeated Measures
MNAR	Missing not at random
MTD	maximal tolerated dose
NINDS	National Institute of Neurological Disorders and Stroke
NSAID	nonsteroidal anti-inflammatory drug
NSRI	non-selective reuptake inhibitor
OD	overdose
PedMIDAS	Pediatric Migraine Disability Assessment
PedsQL 4.0	Pediatric Quality of Life Inventory, Version 4.0
PPS	Per Protocol Analysis Set
PK	pharmacokinetic
PREA	Pediatric Research Equity Act
PT	preferred term
QD	once a day
QTcF	QT interval corrected using Fridericia's method
RR	respiratory rate
SADR	suspected adverse drug reaction
SAE	serious adverse event
SAP	statistical analysis plan
SD	standard deviation
SM	study medication
SOC	system organ class
SOP	standard operating procedure
SSRI	serotonin selective reuptake inhibitors
TEAE	treatment-emergent adverse event
TPM	topiramate
TPM XR	topiramate extended release
US	United States
WBC	white blood cell
WHO DD	World Health Organization Drug Dictionary
XR	extended release

1 INTRODUCTION

Migraine is a disabling primary headache disorder characterized by recurrent attacks of predominantly unilateral headache that is pulsatile in nature, moderate to severe in intensity, and often aggravated by routine physical activity. Migraine affects up to 15% of the world population (Stovner et al., 2007). Recurrent headache is one of the most common complaints among children and adolescents, with an estimated 75% of children reporting significant headache by the age of 15 years (Antonaci et al., 2014). Moreover, approximately 4% to 11% of children between the ages of 7 and 11 years are affected by migraine, with one-third of pediatric patients meeting the criteria for pharmacologic prophylaxis (Lewis et al., 2004). The International Classification of Headache Disorders, 3rd edition (ICHD-3) summarizes definitions and diagnostic criteria for migraine with and without aura, as well as special features that are characteristic of migraine headaches in children and adolescents (Appendix 10.1).

Symptomatic manifestations of migraine are often different between adults and children. Pediatric migraine attacks are more often bilateral, of shorter duration than in adults, and have a higher prevalence of gastrointestinal complaints such as nausea, vomiting and pain (Kacperski, Kabbouche, O'Brien, & Weberding, 2016). Recurrent migraine attacks are associated with significant functional impairment, resulting in poor long-term educational, occupational, and social outlook and reduced life satisfaction (Powers, Patton, Hommel, & Hershey, 2003). The long-term outcome of childhood headaches and their progression to chronic conditions is unknown.

Treatment and management of migraine require a multilevel approach, including medication management of acute episodes, prophylactic treatment for frequent and disabling headaches, and non-pharmacologic approaches, such as cognitive and behavioral therapies, lifestyle modifications, and trigger avoidance strategies, to facilitate better therapeutic outcomes. In general, pharmacologic preventive therapies are indicated when other approaches have been ineffective (Bonfert et al., 2013).

Topiramate (TPM), an antiepileptic drug (AED), is the only drug indicated for migraine prophylaxis in the pediatric patient population, specifically for children and adolescents ≥ 12 years of age. The efficacy and safety of TPM in migraine prophylaxis have been clearly demonstrated in several randomized, double-blind, placebo-controlled trials in thousands of patients (Jackson et al., 2015). These studies have provided consistent evidence that TPM reduces migraine frequency and acute medication use, improves quality of life, and reduces disability in patients with episodic and in those with chronic migraine, with or without medication overuse headache. As a result, TPM has become the most commonly prescribed migraine preventative in adults and is frequently recommended for migraine prophylaxis in children and adolescents (Kacperski et al., 2016; Silberstein, 2017).

Trokendi XR® (SPN-538) was developed by Supernus Pharmaceuticals as an extended release (XR) formulation of topiramate (TPM XR), a once a day (QD) product designed to be equivalent to TPM immediate release (IR) (Topamax®, Janssen Pharmaceuticals, Inc.) administered twice daily. Currently, Trokendi XR is marketed as an AED (monotherapy and adjunctive therapy) for patients 6 years of age and older and as a preventive for migraine headaches in adults and adolescents 12 years of age and older ("[National Institutes of Health-DailyMed- Trokendi XR- Prescribing Information.](#)," 2022). United States (US) Food and Drug Administration (FDA) approval of Trokendi XR was based on the product's demonstrated bioequivalence to Topamax.

The safety and tolerability of TPM has been studied extensively in adult and pediatric patients with epilepsy but has not been definitively established for prophylaxis of migraine headache in patients younger than 12 years of age. In a meta-analysis of randomized clinical trials of TPM in children with migraine <18 years of age, the most frequently reported adverse events (AEs) included paresthesia, upper respiratory tract infections, fatigue, weight decrease, anorexia, and cognitive impairments ([Le, Yu, Wang, Ali, & Guo, 2017](#)). Most AEs, including those leading to discontinuation of TPM, occurred during the titration period and did not worsen during maintenance ([Lainez et al., 2007](#)). In pediatric patients, slow dose titration is recommended to alleviate AEs, and dose reductions may improve treatment compliance.

In previous migraine studies MIGR-001 ([Silberstein, Neto, Schmitt, Jacobs, & Group, 2004](#)), MIGR-002 ([Brandes et al., 2004](#)), MIGR-003 ([Diener et al., 2004](#)), and MIG-3006 ([Lewis et al., 2009](#)), most AEs reported with the use of TPM were mild to moderate in severity, and no unusual or unexpected safety risks were identified. However, long-term TPM treatment requires continuous assessment for AEs that are specifically attributable to this drug. These include ophthalmologic side effects (acute myopia, secondary angle closure glaucoma, and visual field defects), oligohydrosis and hyperthermia, treatment-related laboratory abnormalities (e.g., metabolic acidosis, hyperammonemia, and changes in complete blood count values), nephrolithiasis, negative effects on growth, and suicidal behavior and ideation.

Monitoring for neuropsychiatric effects and cognitive impairment is of crucial importance because of the effect of TPM on cognitive function, specifically on concentration/attention, memory, and speech/language abilities. This risk for cognitive adverse reactions is dose dependent and is greater in younger pediatric patients (6 to 11 years) than in older children (12 to 17 years) ("[National Institutes of Health-DailyMed- Trokendi XR- Prescribing Information.](#)," 2022; "[National Institutes of Health-DailyMed- Topamax- Prescribing Information.](#)" 2022).

Trokendi XR is an approved agent for the prophylaxis of migraine in adults and adolescents 12 years of age and older; however, its efficacy as a migraine preventative has not been established in the 6-to-11 year age range. In this study (538P401), the efficacy and safety of Trokendi XR as a preventative therapy for migraines in this younger pediatric population will be explored. The XR formulation of SPN-538 is expected to be beneficial in this patient population where, compared to the IR TPM products, it offers more constant plasma drug concentrations, less frequent dosing, and an improved AE profile ([Silberstein, 2017](#)).

2 STUDY OBJECTIVES AND ENDPOINTS

2.1 Primary Objective

To evaluate the treatment effect of SPN-538 compared to placebo in reducing MMDs in children 6 to 11 years old with migraine.

2.2 Secondary Objectives

To assess the efficacy of SPN-538 treatment on the following:

1. Responder rate with a responder defined as a subject with at least a 50% reduction in monthly migraine days (MMDs).
2. Number of days per month requiring acute rescue medication.
3. Monthly rate of total headache days (migraine and non-migraine), duration and severity.
4. Onset of action, defined as the time to first statistically significant treatment effect observed and maintained until the end of study (EOS).
5. Headache Disability Score as measured by the Pediatric Migraine Disability Assessment (PedMIDAS).
6. Health-related quality of life (HRQoL) as measured by the Pediatric Quality of Life Inventory, Version 4.0 (PedsQL 4.0), for the self-report and parent-report.

Primary Estimand

According to the International Conference on Harmonisation (ICH) E9 Addendum, the attributes of the primary estimand (target of estimation) are provided below.

1. Treatment: To compare the treatment effect of SPN-538 vs placebo.
2. Population: The population targeted for the scientific question is defined via the inclusion and exclusion criteria in children 6 to 11 years old (inclusive) with a history of migraine.
3. Variable: The primary efficacy endpoint is the change from baseline in the monthly (28-day) rate of migraine days during the last 4 weeks of the 20-week double-blind Treatment Phase relative to the Prospective Baseline Period based on the Full Analysis Set (FAS) as defined in [Section 7.3](#).
4. Intercurrent event (ICE): For subjects discontinued due to AE or lack of efficacy, missing data will be imputed using MI under the MNAR assumption. For all other missing data due to ICE, missing data will not be imputed following the treatment

[figure not shown]
policy strategy, which assumes that ICE did not occur. Methods of handling missing data are described in [Section 7.2](#).

5. Population level summary: The difference in the mean change from baseline in the monthly (28-day) rate of migraine days during the last 4 weeks of the Treatment Phase between the SPN-538 and placebo groups will be analyzed using a MMRM as discussed in [Section 7.8.1](#).

2.3 Safety Objective

To evaluate the safety and tolerability of SPN-538 in children 6 to 11 years old as assessed by:

1. Incidence of AEs.
2. Clinical laboratory tests (blood chemistry and hematology, urinalysis).
3. Vital signs, physical and neurological examinations, and electrocardiograms (ECGs).
4. Columbia Suicide Severity Rating Scale (C-SSRS) assessment.
5. Cognitive Assessment.

2.5 Primary Endpoint

The primary efficacy outcome measure is the change in the monthly (28-day) rate of MMDs during the last 4 weeks of the 20-week double-blind Treatment Phase relative to the Prospective Baseline Period.

- 28-day rate of Migraine Days = (total number of migraine days during the last 4 weeks of the double-blind treatment phase/total number of days during the last 4 weeks of the double-blind treatment phase) *28.
- Prospective Baseline = total number of migraine days in the last 28 days prior to randomization.

A migraine day is defined as a calendar day (12:00 am to 11:59 pm) in which the subject experiences a migraine attack that starts, ends, or recurs within 24 hours and lasts for ≥ 1 hour (if untreated) or ≥ 30 minutes (if interrupted with rescue medication). Pain persisting for more than 1 calendar day (≥ 24 hours) after initial onset will be considered as a new, distinct headache day. **MMDs is defined as the number of migraine days within 28 days or 4 weeks.**

2.6 Secondary Endpoints

The secondary efficacy endpoints are:

1. Responder, defined as a subject with $\geq 50\%$ reduction in the MMDs during the last 4 weeks of the Treatment Phase relative to Prospective Baseline Period.

2. Change from baseline in the monthly migraine-specific acute rescue medication use in the last 4 weeks of the Treatment Phase.
3. Change in the monthly rate of total headache days (migraine and non-migraine), duration and severity.
4. Change in the time to onset of action, defined as the time to first statistically significant treatment effect observed and maintained until the EOS.
5. Change from baseline in the Headache Disability Score as measured by PedMIDAS during the last 4 weeks of the Treatment Phase.
6. Change from baseline in the HRQoL as measured by the PedsQL 4.0 Total Scale Score during the last 4 weeks of the Treatment Phase for the self-report and the parent-report.

The safety endpoints are:

1. Incidence of AEs.
2. Clinical laboratory test results (blood chemistry and hematology, urinalysis).
3. Vital signs, physical and neurological examinations, and ECGs.
4. C-SSRS assessment.
5. Cognitive Assessment.

3 INVESTIGATIONAL STUDY PLAN

3.1 Overall Study Design and Plan

This is a multicenter, randomized, double-blind, placebo-controlled, 2-arm, parallel group Phase 4 study in children 6 to 11 years of age to evaluate the efficacy and safety of SPN-538 for the prevention of migraine. SPN-538 (or matching placebo) will be administered as a single oral dose QD, starting at 25 mg/day and increasing every 2 weeks in 25 mg increments to a target dose of 2 to 3 mg/kg/day or the maximum tolerated dose (MTD), whichever is less. The total study duration is a maximum of 34 weeks, including a Screening Period and a Prospective Baseline Period of up to 8 weeks; a Treatment Phase of 20 weeks (8 weeks titration followed by 12 weeks of maintenance dosing); a Dose Tapering Period of 1 to 3 weeks; and a Safety Follow up period of 1 to 3 weeks. Approximately 35 sites in the United States (US) are planned. The study schematic is shown in [Figure 1](#) and described below.

Pre-treatment Phase

Screening Period (Visit 1, up to 8 weeks before Visit 3)

At Visit 1, informed consent and informed assent (if applicable) will be obtained. Initial screening evaluation includes headache history, medical, family and psychiatric histories, ECG and vital sign assessments, physical and neurological examinations,

concomitant medications, headache disability, and laboratory tests including hematology, chemistry, urinalysis, drug screen, and serum pregnancy test (females of childbearing potential [FOCPs] only). Suicidality will be evaluated using the C-SSRS, Children's version. A visual neurological examination will also be required prior to Visit 2 ([Section 6.8.5](#)).

Subjects treated with the following prophylactic medications should discontinue the treatment 14 days prior to the Prospective Baseline Period: antipsychotics, antimanics, barbiturates, benzodiazepines amitriptyline, lithium, valproic acid, tricyclic antidepressants, AEDs, calcium channel blockers, sedatives, serotonin selective reuptake inhibitors (SSRIs), non-selective reuptake inhibitor (NSRIs), calcitonin gene-related peptide (CGRP) receptor antagonists, cannabidiol (CBD) oil, herbal preparations/supplements such as feverfew or St John's wort and/or any medications that could impair or decrease thinking and concentration. It is recommended to taper off antipsychotics, barbiturates, benzodiazepine, tricyclic antidepressants, lithium, amitriptyline, valproic acid, SSRIs and NSRIs as applicable ([Appendix 10.10](#)).

Note: Subjects must refrain from using these medications throughout the duration of the study.

Non-pharmacologic approaches involving life-style modifications are allowed if initiated more than 1 month prior to Screening.

For subjects who met the eligibility criteria, prophylactic migraine treatments will be allowed if on a stable dose for at least 12 weeks prior to the Screening Visit including daily nonsteroidal anti-inflammatory drugs (NSAIDs), antiemetics, antihistamines, corticosteroids (i.e., systemic inhaled, or topical), high-dose magnesium supplements (≥ 600 mg/day), high-dose riboflavin (≥ 100 mg/day), coenzyme Q10, omega-3, melatonin, muscle relaxants and β -blockers ([Appendix 10.9](#)).

Note: The dose and the medication must remain stable (7 days/week) during the duration of the study.

During Screening, acute rescue medications (e.g., ibuprofen, acetaminophen, ergot derivatives and triptans) will be allowed for symptomatic relief of headaches (migraine and non-migraine) as long as the pattern of use remains stable and does not meet the criteria for medication overuse (i.e., > 10 treatment days/month for ergot-containing medication or triptans; > 15 treatment days/month for simple analgesics/NSAIDs). The use of narcotics is not permitted.

Re-screening is not permitted, however subjects who screen failed due to a PedMIDAS Total score > 50 under any prior version of the protocol, may be rescreened if they still meet the study eligibility criteria under this version of the protocol (Version 4.0, 14 Dec 2022).

Placebo Training

During Visit 2, caregivers will be asked to complete a training on the placebo effect. The training consists of three parts to be completed using the iPad: Part 1 (10 questions) illustrates what is the placebo effect (e.g., 'What is a placebo?', 'Who knows whether your child is getting the study drug or the placebo?'); while Part 2 (6 questions) describes the importance of understanding how to use the study application/diary (e.g., 'What is the study application used for?', 'Who is collecting the data in the study application?') and Part 3 (8 questions) highlights the importance of providing accurate information about the study (e.g., 'What is a pediatric migraine?', 'What's the purpose of the trial?').

For any incorrect answer during the training, the next page will provide an explanation and the correct answer.

Refresher placebo training will be administered at Visits 4 and 6.

Prospective Baseline Period (Visit 2, 4 weeks before Visit 3)

[figure not shown]
At Visit 2, the subject's parent or guardian will be asked to maintain a daily electronic Headache Diary (completed by the parent with the subject's assistance) in which they will record daily headache-associated symptoms and the duration and severity of all headaches. Rescue medication usage during the 28-day Prospective Baseline Period will also be recorded in the diary. Vital signs, concomitant medications, clinical laboratory tests, urine pregnancy test (FOCP only) and suicidality evaluation using the C-SSRS will be obtained at the visit.

Treatment Phase

Randomization (Visit 3, Day 1)

Upon completion of the Prospective Baseline Period, eligibility for randomization will be determined based on 1) the number of migraine episodes (must be 3-12 inclusive) during the Prospective Baseline Period, *and* 2) the number of total headache days (migraine and non-migraine; no more than 14 headache days) during the Prospective Baseline Period as observed and recorded using the Headache Diary.

All eligible subjects will be randomized in a blinded fashion by the interactive web response system (IWRS) in a 1:1 ratio of placebo or SPN-538. Subjects will receive a 4-week supply of their assigned study medication (SM). Safety evaluations including AEs, vital signs and suicidality evaluation (using the C-SSRS), eye examinations, concomitant medications, urine pregnancy test (FOCP only), headache disability, HRQoL, and cognitive assessments will be obtained at the visit. SM accountability and resupply will occur at each subsequent study visit.

Maintenance Period (Visits 6 to 8, Weeks 9 to 20)

Once the target dose or MTD is reached, treatment at that dose will continue for the 12 weeks of the maintenance period; up to one dose reduction will be allowed for safety

and tolerability during this period. Additional dose titration related to body weight changes will be reviewed and approved by the Medical Monitor and the Sponsor on a case by case basis. The number, severity, and symptoms of all headaches, as well as the type and dose of rescue medication and SM compliance will be recorded daily in the Headache Diary. During the Maintenance Period, clinic visits will be scheduled every 4 weeks. During each clinic visit, a 4-week supply of SM will be provided, and SM compliance and the Headache Diary will be reviewed. Safety evaluations, including vital signs, concomitant medications, cognitive assessment, C-SSRS, clinical laboratory tests (only at Visit 8), urine pregnancy test (FOCP only), urine drug screen, physical and neurological evaluations will also be performed. [REDACTED]

[REDACTED]

During Visit 6, the eye exam will be performed, and another refresher placebo training will be administered.

Telephone contacts will occur at the intervening 2-week periods [Days 71, 99 and 127 (± 2 days)] between clinic visits for safety assessment and to provide guidance on dose reduction (as needed).

Post-Treatment Phase

Tapering Period (Weeks 21 to 23):

During the following 3 weeks the dose of SM will be gradually reduced until the subject is no longer taking the SM, so that by the end of Week 23 the subject is out of SM. Dose tapering will also be required for subjects who discontinue early during the titration period (Week 3 through Week 8) or maintenance period (Week 9 through Week 20). Subjects who discontinue early at an MTD of 25 mg/day will not undergo a dose tapering period but will return to the clinic to complete the EOS procedures (all procedures scheduled to be performed at Visit 9) within 1 week after discontinuation of SM.

End of Study (Visit 9):

[figure not shown]
All subjects who complete the study (Week 20) will return to the clinic for a final safety evaluation at the end of the Tapering Period (Visit 9). During this visit, subjects will complete the EOS procedures: clinical laboratory tests, AE assessments, vital signs, concomitant medications review, ECG, physical and neurological evaluations, eye exam, urine pregnancy test (FOCP only) and urine drug screen, headache disability, HRQoL, C-SSRS and cognitive assessments. The remaining SM and the Headache Diary device, if applicable, will be collected, and safety follow-up instructions will be provided to caregivers.

Safety Follow-up Telephone Call (Weeks 24 to 26):

Safety follow-up over the telephone will take place 1 to 3 weeks after the EOS/early termination (ET) visit. During the telephone call, all concomitant medications, cognitive assessment and AEs will be evaluated and recorded. Any subject who experiences an AE (whether serious or non-serious) or has a clinically significant abnormal laboratory test value will be followed by the Investigator for up to 30 days after the EOS/ET visit. These subjects will be treated and/or followed up until the symptoms or laboratory values return to normal/baseline or acceptable levels, as determined by the Investigator.

Figure 1 Study Schematic

EOS = end of study; V = visit

- Dosing will be based on weight and is flexible. [REDACTED]. [REDACTED]. [REDACTED]. The total daily dose will not exceed 100 mg/day (or 4 × 25 mg capsules/day). In the event of tolerability problems during titration, the Investigator may reduce the dose by 25 mg/week after Week 3. During maintenance, up to one dose reduction will be allowed for safety and tolerability during this period. Additional dose titration related to body weight changes will be reviewed and approved by the Medical Monitor and the Sponsor on a case by case basis.
- Subjects will receive a follow-up telephone call 1 to 3 weeks following discontinuation of study medication (Visit 9/EOS or early termination).

This document is confidential. It contains proprietary information of Supernus® Pharmaceuticals, Inc. Any viewing or disclosure of such information that is not authorized in writing by the Sponsor is strictly prohibited. Such information may be used solely for the purpose of reviewing or performing this study.

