3.3.3 Exclusion Criteria

1. Subjects with chronic migraine (>14 headache days per month), cluster headaches, or migraine aura without headache, and who are unable to distinguish migraines from other headache types.
2. Subjects with more than 14 headache days during the 28-day Prospective Baseline Period (based on the Headache Diary).
3. Have taken any disallowed migraine preventive medication including TPM within 14 days prior to the start of the Prospective Baseline Period; or used onabotulinumtoxinA (Botox[®]) within 3 months prior to entering the Screening period.
4. Previously failed to respond to TPM prophylaxis therapy using an adequate dose (2 to 3 mg/kg/day) for an adequate period of time (minimum of 3 months), or those who have previously discontinued TPM due to AEs within 6 months prior to Screening.
5. Previously failed more than 2 adequate clinical trials (defined as at least 1 month of treatment at a full therapeutic dose) of an established prophylactic anti-migraine regimen within 6 months prior to Screening.
6. Known history of allergic reaction or anaphylaxis to TPM.

7. Overuse of analgesic or migraine-specific agents for acute treatment of migraine defined as:
 - a. >10 treatment days/month of ergot-containing medications or triptans;
 - b. >15 treatment days/month with simple analgesics (including NSAIDs)
 - c. Use of narcotics
8. Subjects treated with the following prophylactic medications should discontinue the treatment 14 days prior to the Prospective Baseline Period: antipsychotics, antimanics, barbiturates, benzodiazepines amitriptyline, lithium, valproic acid, tricyclic antidepressants, AEDs, calcium channel blockers, sedatives, SSRIs, NSRIs, CGRP receptor antagonists, CBD oil, herbal preparations/supplements such as feverfew or St John's wort and/or any medications that could impair or decrease thinking and concentration. It is recommended to taper off antipsychotics, barbiturates, benzodiazepine, tricyclic antidepressants, lithium, amitriptyline, valproic acid, SSRIs and NSRIs as applicable.
Note: Subjects must refrain from using these medications throughout the duration of the study.
9. Subjects using non-pharmacologic complementary and alternative prophylactic approaches for migraine prevention, such as neuromodulation, acupuncture, behavioral interventions, spinal manipulation, occipital nerve block and neurofeedback.

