3.4.1 Discontinuation of Subjects

Subjects who discontinue early will complete the procedures listed for Visit 9 ([Section 5.1.6](#)).

The Investigator(s) or subjects/caregivers may stop SM treatment at any time for safety or personal reasons. The subject's caregiver is free to withdraw their child from the study at any time for any reason without prejudice to their future medical care by the physician or at the institution. The Sponsor may also withdraw the subject at any time in the interest of subject safety. The withdrawal of a subject from the study should be discussed where possible with the Medical Monitor and/or clinical research associate (CRA) before the subject discontinues taking SM. Subjects removed from the study for any reason will not be replaced.

Reasons for subject discontinuation may include:

- Withdrawal of consent and assent
- Non-compliance with study procedures
- Lack of efficacy
- Investigator decision
- Occurrence of unmanageable AEs
- Lost to follow-up
- Other (study is terminated by the Sponsor, blind is broken, subject has relocated or death etc.)

The primary reason for subject discontinuation must be recorded in the electronic case report form (eCRF). If a subject is withdrawn for more than one reason, each reason

should be documented and the most medically significant reason should be entered on the eCRF.

If a subject misses any doses of SM during this study, the Investigator shall counsel the subject's caregiver on the importance of adherence. If the subject has consistently missed doses, he or she may be discontinued from the study at the discretion of the Investigator and in consultation with the Medical Monitor and the Sponsor; all procedures for discontinuation will be followed.

Efforts will be made by the study site staff to discuss with the parents/caregivers the meaning of adherence on the completion of the daily diary as at least 70% compliance with the migraine diary is requested.

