4.4 Method of Assigning Subjects to Treatment Group

Eligible subjects will be randomized in a 1:1 ratio at Randomization Visit (Visit 3) to receive either SPN-538 or placebo. Randomization will be stratified by number of migraine days (high vs. low) at baseline to ensure treatment balance in each stratum. High monthly migraine stratum will be defined as 6 to 14 migraine days observed during the 28-day Prospective Baseline Period; and low monthly migraine stratum will be defined as 3 to < 6 migraine days during the 28-day Prospective Baseline Period.

Treatment A: Placebo

Treatment B: SPN-538

Allocation of study treatment will occur centrally via an IWRS using a randomization schedule to determine the SM assignment for each subject being randomized.

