## 5. Study Variables

### 5.1. Primary Efficacy Variable

The primary efficacy endpoint of this study is the change in the monthly (28-day) rate of migraine days (MMDs) during the last 4 weeks of the 20-week double-blind Treatment Phase relative to the Prospective Baseline Period.

The 28-day rate of monthly migraine days (MMDs) days is calculated during the last 4 weeks of Doble-blind (DBL) period as

$$\frac{\# \text{ of days of migraine}}{\# \text{ of days with nonmissing headache record in the diary}} \times 28.$$

The 28-day rate of MMDs for the prospective baseline period is calculated as in above during the last 4 weeks of ‘prospective baseline’.

For MMRM analysis described in Section 7.1, the 28-day MMDs will be calculated for each visit window as depicted in the following Table.

Visit Window	Analysis Visit	Analysis Month
$2 \leq \text{Visit} \leq 3$	V3 (Prospective baseline)	Month 0
$\text{Visit } 3 < \text{to} \leq \text{Visit } 4$	V4 (Titration period 1)	Month 1
$\text{Visit } 4 < \text{to} \leq \text{Visit } 5$	V5 (Titration period 2)	Month 2
$\text{Visit } 5 < \text{to} \leq \text{Visit } 6$	V6 (Maintenance period 1)	Month 3
$\text{Visit } 6 < \text{to} \leq \text{Visit } 7$	V7 (Maintenance period 2)	Month 4
$\text{Visit } 7 < \text{to} \leq \text{Visit } 8$	V8 (Maintenance period 3)	Month 5

The 28-day MMDs will not be calculated after Visit 8. In other words, data from the Tapering period will not be included.

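### Baseline eligibility and the randomization stratum use raw diary counts with no minimum number of recorded days, while SAP 5.1 rescales the same baseline to recorded days

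*Protocol*

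**What the plan says.** **Eligibility.** Protocol 3.1 (Randomization) and inclusion criterion 3 require 3 to 12 migraine episodes in the Prospective Baseline Period. They also cap "the number of total headache days (migraine and non-migraine; no more than 14 headache days) during the Prospective Baseline Period as observed and recorded" in the diary. Exclusion criterion 2 repeats the cap: "Subjects with more than 14 headache days during the 28-day Prospective Baseline Period (based on the Headache Diary".

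**Stratum.** Protocol 4.4, repeated in SAP 3.4.4, gives two strata. The upper one reads: "High monthly migraine stratum will be defined as 6 to 14 migraine days observed during the 28-day Prospective Baseline Period". A child with at least 3 but fewer than 6 such days goes to the lower one. Both are counts.

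**Diary completeness.** Protocol 3.4.1 and SAP 3.3 say that "at least 70% compliance with the migraine diary is requested". This stands in the text on discontinuation and adherence. It is not an inclusion, exclusion or randomization condition. Protocol 5.1.3 has the diary reviewed for eligibility at Visit 3 and states no completeness threshold.

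**Baseline for analysis.** There are three definitions:
- Protocol 2.5 uses a count: "Prospective Baseline = total number of migraine days in the last 28 days prior to randomization".
- SAP 5.1 divides migraine days by the number "of days with nonmissing headache record in the diary" and multiplies by 28. It applies this to baseline too: "The 28-day rate of MMDs for the prospective baseline period is calculated as in above during the last 4 weeks of" that period. SAP 5.2 does the same for total headache days.
- SAP section 4, item 2 divides by the total number of days before randomization, whether recorded or not.

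**The concern.** A raw count gives an unrecorded day no headache. SAP 5.1 and 5.2 instead drop that day from the denominator. A child with gaps in the baseline diary therefore has one baseline for eligibility and stratum and another for analysis, and the fuller the gaps, the further apart they are.

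The ceiling of 14 headache days is the prospective check that keeps the trial to episodic migraine. As written, it is easier to meet with a sparse diary. At the extreme, a diary with 14 or fewer entries cannot exceed it. The stratum, which is there to balance baseline migraine days, then depends partly on how completely the family recorded.

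**Working it through.** The plan gives no figure for baseline diary completeness, so there is none to reproduce. The sample size (117 per arm, 234 completers, 276 randomized) is not in dispute and does not change.

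**1. The two scales side by side.** Inputs: the ceiling of 14 (Protocol 3.1), the stratum cut at 6 (Protocol 4.4), and the SAP 5.1 formula, rate = count × 28 / d, where d is the number of recorded days. The requested 70% of 28 is 19.6, so d = 20 is the lowest whole number that meets it.

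| d | SAP rate for 14 recorded headache days | SAP rate for 5 recorded migraine days |
|---|---|---|
| 28 | 14.0 | 5.0 |
| 26 | 15.1 | 5.4 |
| 24 | 16.3 | 5.8 |
| 22 | 17.8 | 6.4 |
| 20 | 14 × 28/20 = 19.6 | 5 × 28/20 = 7.0 |

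At d = 20, every recorded count from 11 to 14 headache days passes the ceiling with an SAP rate of 15.4 to 19.6. Five recorded migraine days mean the low stratum, yet the SAP rate reaches 6 once d is 23 or less (5 × 28/23 = 6.09).

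**2. How often this happens for a given child.** The documents give no baseline missing rate, so d is varied. Assume days are missing at random within the 28. With T true days, the recorded number X is hypergeometric (28 days, T events, d drawn).

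Hand check at d = 26: there are C(28,2) = 378 ways to miss two days. A child with 16 true headache days records 14 only if both missed days are headache days: C(16,2)/378 = 120/378 = 0.32. A child with 7 true migraine days records 5 only if both missed days are migraine days: C(7,2)/378 = 21/378 = 0.06.

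| d | P(X ≤ 14), 16 true headache days | P(X ≤ 14), 18 true headache days | P(X < 6), 7 true migraine days |
|---|---|---|---|
| 28 | 0 | 0 | 0 |
| 26 | 0.32 | 0 | 0.06 |
| 24 | 0.80 | 0.15 | 0.25 |
| 22 | 0.96 | 0.64 | 0.48 |
| 20 | 0.996 | 0.92 | 0.67 |

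The last column is the chance of falling below the high-stratum cut. At d = 20 it includes about 0.01 for children recorded below 3, who would be in neither stratum.

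**3. The lower limit.** Treating each episode as one day, a child with 3 true episodes records fewer than 3 with probability 0.21 at d = 26 and 0.65 at d = 20. With 4 true episodes the figures are 0.02 and 0.32.

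**4. Would rescaling the ceiling cure it?** Applying the ceiling to the SAP rate means X ≤ d/2. A child with 14 true headache days, who is eligible, would then be rejected with probability C(14,2)/378 = 91/378 = 0.24 at d = 26 (limit 13) and 0.34 at d = 20 (limit 10). Under the raw count that probability is 0. The floor errors do not change for d of 20 or more: two recorded episodes in 20 days scale to 2 × 28/20 = 2.8, still below 3.

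**The case against.** **Missing days may be few.** Protocol 6.1 calls for an entry every day, headache or not, with reminder alarms, and the diary is reviewed at Visit 3. With 26 days recorded the errors are modest and with 28 they vanish. This stands. The result is a range, and the values at 20 days must not be read as typical. Nor does the protocol accept 70% at baseline; it asks for at least that in general adherence text.

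**Missingness may not be random.** The diary form in Appendix 10.2 is worded for days with a headache. If skipped days are mostly headache-free, the raw count is nearer the truth and the SAP rate overstates. This stands as a limit on the probabilities. It does not remove the conflict between the two scales.

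**Other gates exist.** Inclusion 3 also caps headache days over the 3 months before Screening, and exclusion 1 bars chronic migraine without reference to the diary. The probabilities above are therefore for passing one gate. A reader might infer that children with chronic migraine will enter in those proportions; the documents do not support that.

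**Unseen text.** The detail of SAP 6.7.1 and 7.1 is not in the public text and may hold a diary-completeness rule for analysis. Such a rule would not govern eligibility or the stratum assigned at randomization.

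**Conclusion.** The point holds in limited form. Eligibility and stratum rest on raw counts with no completeness condition, and three baseline definitions stand in the documents. They diverge as soon as baseline days are missing: at 20 recorded days, by up to 5.6 headache days at the ceiling (19.6 against 14). The chance that a child with 16 true headache days passes this gate runs from 0 with a full diary to 0.996 at 20 days; for 7 true migraine days falling below the high-stratum cut it runs from 0 to 0.67. Both ranges assume randomly missing days and an unknown missing rate.

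Two stronger readings should be resisted. First, the treatment comparison is not biased: the error arises before randomization, does not depend on arm, and the primary model (Protocol 7.8.1) adjusts for the continuous baseline rate and lists no stratum term. Second, a high SAP rate does not by itself mean a wrong stratum: 12 migraine days in 20 is 16.8 per 28, above the stated upper bound of 14 but still on the high side of the cut at 6. What is lost is a clear target population, some of the stratified balance, and precision in the baseline covariate.

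**What to change.** 1. In Protocol 3.1, inclusion 3, exclusion 2 and section 4.4, require a stated minimum number of recorded baseline diary days before randomization, programmed in the e-diary/IWRS eligibility report. At least 20 of 28 matches the protocol's own 70%. This bounds the mismatch but does not remove it: a child recorded at the ceiling could still have a rate of 19.6. A higher minimum leaves less: 16.3 at 24 days, 15.1 at 26.
2. Use one baseline definition for the stratum and the analysis, by reconciling Protocol 2.5 and 4.4 with SAP section 4 item 2 and SAP 5.1.

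The cost is a short amendment and one programmed rule. The downside is that a few children with sparse diaries cannot be randomized, and more of them with a higher minimum.

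Rescaling the ceiling itself is optional. It admits fewer children above 14 true days but newly rejects some at or just below 14 (24% to 34% of those with exactly 14, at 26 and 20 recorded days), and it leaves the floor errors as they are at 20 or more recorded days.
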